6.4 Six-month Evaluation appointment

Marginal integrity of the restorations and post-operative sensitivity were evaluated using the FDI SQUACE criteria and the USPHS criteria. An intraoral digital photograph of the restoration was also taken. A 6-month follow-up 3D OCT scan of the restoration and the tooth was done using the same method as described in Section 6.3.

6.5 Eighteen-month Evaluation appointment

Marginal integrity of the restorations and post-operative sensitivity were evaluated using the FDI SQUACE criteria and the USPHS criteria. An intraoral digital photograph of the restoration was also taken. A 6-month follow-up 3D OCT scan of the restoration and the tooth was done using the same method as described in Section 6.3. In addition to these, a single bite-wing digital radiograph was obtained during the appointment.

7.0 Withdrawal of Participants

Participants could withdraw at any time during the study. If the participant wished to withdraw, they were thanked, advised that data already provided was maintained and the participant was withdrawn from the study with no effect on their continued relationship with the UMN and UMN SOD.

8.0 Risks to Participants

The dental composite restoration procedure is considered standard of care and includes standard procedures that are involved in the provision of a dental restoration and hence considered of minimal risk. In addition, participant wore a scan guide during OCT scanning and the process took between 3-5 seconds.

9.0 Data Analysis

9.1 Power Analysis:

Sample size calculation was based on the clinical success rate of posterior class I composite restoration observed in a previous study [16]. Using a significance level of 0.05, power of 80%, and equivalence limit of 15%, the sample size required was 10 restorations per group. However, as the restorative technique of this study is different from the previous study [16], the number of restorations was increased to 15 per group and to account for potential dropouts, the sample size was further increased to 18 per group.

9.2 Statistical Analysis

Descriptive analysis of the FDI criteria, USPHS criteria and OCT outcome measure for marginal defects for each group was performed.

For comparison between groups with FDI and USPHS criteria, the Mann-Whitney test was used, all with alpha = 0.05.

For comparison between groups with OCT outcome measure, the Shapiro-Wilk test was used to determine the distribution of the data and it was found the data was not normally distributed. Hence the non-parametric Mann-Whitney test was used to compare the prevalence of the three OCT outcome measures of the two groups.

10.0 Results

10.1 Descriptive

Thirty-six restorations were placed in premolars and molars. In total, 2 recalls (6-months 18 - months) were performed after baseline assessment. There were 3 dropouts at the 6 months follow up yielding a dropout rate of 8.3%. Reasons for dropping out was moving to another city.

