3.0 Study Outcome Measures

3.1 Primary Outcome Measures

The study's primary outcome measures include the following:

Evaluation and comparison of the short-term marginal integrity, up to 18-months, of two Class I composite preparation techniques using the FDI World Dental Federation and US Public Health Service criteria for marginal integrity of dental composite restorations.

Primary assessment endpoints

- 1. Marginal staining FDI³ and USPHS⁴ criteria
- 2. Marginal irregularities FDI³ and USPHS⁴ criteria

3.2 Secondary Outcome Measures

Evaluation and comparison of the short-term marginal integrity, up to 18-months, of two Class I composite preparation techniques using OCT backscattered intensity outcome measures for marginal integrity.

- 1. Elevated OCT reflectance of the occlusal cavosurface angle.
- 2. Elevated OCT reflectance along tooth-restoration interface.
- 3. Diminished OCT reflectance along tooth-restoration interface.

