10.2 Marginal Staining (Primary Outcome Measure 1)

No marginal staining was observed with either the USPHS (Table 1) or FDI (Table 2) criteria, in any of the restorations of either group for all three time points (Table 3). Hence statistical analysis was not performed.

Score	Criteria
А	None
В	Superficial staining (removable, usually localized).
С	Deep staining (not removable, generalized).

Table 1 - USPHS Criteria for Marginal Staining

Table 2 - FDI Criteria for Marginal Staining

Score	Category	Criteria
1	Clinically excellent	No marginal staining.
2	Clinically good	Minor marginal staining, easily removable.
3	Clinically satisfactory	Moderate marginal staining, not aesthetically unacceptable.
4	Clinically unsatisfactory	Pronounced marginal staining, major intervention necessary.
5	Clinically poor	Deep marginal staining, not accessible for intervention.

Table 3 –	Clinical	evaluation	of margina	l staining at	baseline.	6- and	18-months follo	ow-up.
1 4010 5	Cinical	•••••••••••••	or margina	i braining ar	000000000000000000000000000000000000000	o ana	10 months rom	/// "

Time a sint	Creare	No of	FDI	USPHS criteria						
1 ime point	Group	Participant	1	2	3	4	5	А	В	С
Deseline	1	18	100	0	0	0	0	100	0	0
Baseline	2	18	100	0	0	0	0	100	0	0
6 months	1	16	100	0	0	0	0	100	0	0
	2	17	100	0	0	0	0	100	0	0
18 months	1	14	100	0	0	0	0	100	0	0
	2	13	100	0	0	0	0	100	0	0

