10.3 Marginal Irregularities (Primary Outcome Measure 2)

With the USPHS criteria (Table 4), the margins of the restorations in both groups were scored as A, i, e., undetectable irregularities, at baseline, 6-months and 18-months follow-up.

With the FDI criteria (Table 5), the restoration margins of both groups were observed to be either excellent or good, i. e., either Score 1 or 2 (Table 6). No restorations were scored higher than 2 at all three time points. At Baseline, both groups have approximately similar percentages of restorations with Score 1 and 2. However, more restorations in Group 2 demonstrated longer lengths of Score 2 (10 - 20% of the perimeter length).

The Mann-Whitney U test was used to compare the prevalence of Score 1, Score 2a (<10% of the perimeter length) and Score 2b (10 – 20 % of the perimeter length) between the two groups. There were no statistically significant differences (P > 0.05) of the prevalence of the FDI Scores 1 and 2 between the two groups at baseline, 6-months and 18-months follow-up.

Score	Criteria
А	Undetectable.
В	Detectable. (V-shaped defect in enamel only or catches explorer going both ways).
С	Detectable. (V-shaped defect to DEJ).

Table 4 - USPHS Criteria for Marginal Adaptation / Irregularities

Table 5 - FDI Criteria fo	r Marginal	Irregularities
---------------------------	------------	----------------

Score	Category	Criteria
1	Clinically excellent	Harmonious outline, no gaps or white lines
2	Clinically good	Slight ditching, slight step, flashes or minor irregularities.
3	Clinically satisfactory	Multiple or major irregularities, ditching, flashes or steps.
4	Clinically unsatisfactory	Larger irregularities or steps. Repair necessary.
5	Clinically poor	Filling is complete- or partially loose but in situ.

Table 6 – Percentage of restoration in each group, with the respective FDI and USPHS scores for marginal irregularities, at baseline, 6- and 18-months follow-up.

		_	FDI Criteria (SQUACE)						USPHS criteria		
Time	Group	No of Particinant	1	2		3	4	5	А	В	С
point		1 articipant		а	b						
Deceline	1	18	38.9	44.4	16.7	0	0	0	100	0	0
Dasenne	2	18	44.4	33.3	22.2	0	0	0	100	0	0
6 months	1	16	75.0	25.0	0.0	0	0	0	100	0	0
0 monuis	2	17	70.6	23.5	5.9	0	0	0	100	0	0
18	1	14	57.1	42.9	0.0	0	0	0	100	0	0
months	2	13	53.8	30.8	15.4	0	0	0	100	0	0

a - <10 % of margin perimeter; b - 10 -20 % of margin perimeter

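### Does Section 10.1 understate attrition by giving loss at 6 months only, when a quarter of the restorations were not examined at 18 months?

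*Combined protocol and SAP*

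**What the plan says.** Section 3.1 defines the primary outcome as marginal integrity "up to 18-months, of two Class I composite preparation techniques using the FDI World Dental Federation and US Public Health Service criteria". Section 9.1 calculates 10 restorations per group. It then says the number was "increased to 15 per group and to account for potential dropouts, the sample size was further increased to 18 per group". Section 9.2 gives the primary comparison: "For comparison between groups with FDI and USPHS criteria, the Mann-Whitney test was used, all with alpha = 0.05". It names no analysis set and no method for missing data.

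Section 10.1 acknowledges both follow-up visits: "In total, 2 recalls (6-months 18 - months) were performed after baseline assessment". It then gives one loss figure, "There were 3 dropouts at the 6 months follow up yielding a dropout rate of 8.3" per cent, and one explanation: "Reasons for dropping out was moving to another city". There is no corresponding sentence for 18 months.

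Section 10.2 reports that no staining was seen "in any of the restorations of either group for all three time points (Table 3" and its companion tables. Section 10.3 says of the FDI irregularity scores: "No restorations were scored higher than 2 at all three time points". Tables 3 and 6 each carry a column with the number of participants by group and visit: 18 and 18 at baseline, 16 and 17 at 6 months, 14 and 13 at 18 months.

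**The concern.** The primary outcome period closes at 18 months, so the loss at that visit is the one a reader most needs. Someone reading only 10.1 would take away 8.3%, while the tables imply three times that. The loss also exceeds the allowance built into 9.1, and both groups finish below the intended 15.

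The sentences in 10.2 and 10.3 carry no count of restorations examined, so they could be taken to describe all 36 placed.

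What would be at stake is outcome-related loss. If restorations that stained, broke down or were replaced were the ones not seen, an observed record of no staining and no score above 2 would look better than the truth. Without reasons for the later absences, the text does not let a reader rule that out.

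**Working it through.** **Inputs.** 36 restorations placed (10.1), one per participant (6.1), 18 per group. Numbers examined come from Tables 3 and 6, which agree.

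**The plan's own figure.** At 6 months: 36 − (16 + 17) = 3, and 3/36 = 8.3%. The stated rate is reproduced. By group it is 18 − 16 = 2 and 18 − 17 = 1.

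**The 18-month figure.** 36 − (14 + 13) = 9, and 9/36 = 25%. By group: 4/18 = 22.2% and 5/18 = 27.8%. The net further loss after 6 months is 16 − 14 = 2 and 17 − 13 = 4, six in all. It is net because someone absent at 6 months might have returned.

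**Are the table counts the real denominators?** The Table 6 percentages at 18 months convert to whole numbers:

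- Group 1: 14 × (57.1%, 42.9%, 0%) = 8, 6, 0
- Group 2: 13 × (53.8%, 30.8%, 15.4%) = 7, 4, 2

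So the percentages were calculated on 14 and 13, and the printed counts are the observed-case denominators.

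**Against the plan.** The allowance was (18 − 15)/18 = 16.7% per group. Actual loss was larger in both groups. The numbers retained, 14 and 13, are below 15 but above the calculated 10.

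**Was loss different between groups?** Fisher's exact test on 14 seen and 4 unseen against 13 seen and 5 unseen gives p = 1.0. With numbers this small, that shows no sign of imbalance but cannot exclude one.

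**What the smaller denominator does to the staining result.** With no events in n, the upper exact 95% limit is 1 − 0.025^(1/n). For n = 27 it is 12.8%; had all 36 been seen with no event, it would be 9.7%. The result is somewhat less precise, and a reader can work this out from Table 3 as printed.

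**How far could the unseen restorations move the irregularity comparison?** Section 10.3 reports only that p exceeds 0.05. Coding the FDI categories as ordered levels and using the tie-corrected normal approximation with continuity correction (my assumptions, since the document states neither), the 18-month comparison of 8/6/0 with 7/4/2 gives p = 0.64. If the nine unseen restorations may take any FDI level (1, 2a, 2b, 3, 4, 5), there are 126 × 252 = 31,752 ways to allocate them, and 177 give p < 0.05. The two one-sided extremes are:

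| Unseen restorations | Counts (1/2a/2b/3 or worse) | p |
|---|---|---|
| All Group 1 at one level of 3 or worse, all Group 2 at Score 1 | 8/6/0/4 v 12/4/2/0 | 0.14 |
| All Group 2 at one level of 3 or worse, all Group 1 at Score 1 | 12/6/0/0 v 7/4/2/5 | 0.02 |

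Limiting the unseen restorations to Scores 1, 2a and 2b would give 15 × 21 = 315 allocations, 5 of them with p < 0.05. That restriction assumes away the failures that unexplained loss leaves open, so the fuller count is the one to use. These are counts of allocations, not probabilities.

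**The case for a change.** The best case for a change is that a table cannot supply reasons. Section 10.1 is where attrition is reported. It names the 18-month recall and then says nothing about who missed it. Section 7.0 covers only the right to withdraw. The remark about moving away directly follows the three 6-month dropouts, so it cannot safely be stretched to the later six. A reader therefore cannot tell a missed visit from a replaced restoration, and that distinction bears on a claim of zero staining. The remedy would also be cheap: a sentence or two.

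Much of this stands. The 18-month loss is not stated in words, the later absences are not clearly explained, and outcome-related loss cannot be excluded from the documents. Nor does the Mann-Whitney calculation settle the matter: a non-significant difference that mostly stays non-significant is not evidence of equivalence, and 9.1 sized the trial on an equivalence limit of 15%.

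The rest is weaker. The prose in 10.2 and 10.3 speaks of what was observed or scored and points to tables with the counts beside each visit. The natural reading is that it covers the restorations examined. The shortfall against 15 matters little, since 15 was itself raised above the calculated 10. It is also not certain that reasons were recorded for everyone, so the extra text might amount to saying that they are unknown.

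**Conclusion.** The concern is accurate in its facts but does not require a change. The one stated attrition figure is right for the visit it names. The larger figure, 9/36 or 25%, follows by subtraction from two tables that print the counts by group and that the results text cites. No analysis depends on the missing sentence: the test, its inputs, the percentages and the reported conclusions would all be the same with it. This is a gap in description that a careful reader or analyst fills from the tables.

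This rests on three things: the table counts are the true denominators, which the whole-number check supports; loss was close to balanced (4 against 5); and the 18-month statements are read as observed-case results. It does not rest on any claim that the unseen restorations resembled those seen, which the documents cannot show. The 18-month findings should be read as applying to 27 of 36 restorations, with the reasons for the net six later losses unknown.

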10.2 Marginal Staining (Primary Outcome Measure 1)

No marginal staining was observed with either the USPHS (Table 1) or FDI (Table 2) criteria, in any of the restorations of either group for all three time points (Table 3). Hence statistical analysis was not performed.

Score	Criteria
А	None
В	Superficial staining (removable, usually localized).
С	Deep staining (not removable, generalized).

Table 1 - USPHS Criteria for Marginal Staining

Table 2 - FDI Criteria for Marginal Staining

Score	Category	Criteria
1	Clinically excellent	No marginal staining.
2	Clinically good	Minor marginal staining, easily removable.
3	Clinically satisfactory	Moderate marginal staining, not aesthetically unacceptable.
4	Clinically unsatisfactory	Pronounced marginal staining, major intervention necessary.
5	Clinically poor	Deep marginal staining, not accessible for intervention.

Table 3 –	Clinical	evaluation	of margina	l staining at	baseline.	6- and	18-months follo	ow-up.
1 4010 5	Cinical	•••••••••••••	or margina	i braining ar	000000000000000000000000000000000000000	o ana	10 months rom	/// "

Time a sint	Creare	No of	FDI	USPHS criteria						
1 ime point	Group	Participant	1	2	3	4	5	А	В	С
Deseline	1	18	100	0	0	0	0	100	0	0
Baseline	2	18	100	0	0	0	0	100	0	0
6 months	1	16	100	0	0	0	0	100	0	0
	2	17	100	0	0	0	0	100	0	0
18 months	1	14	100	0	0	0	0	100	0	0
	2	13	100	0	0	0	0	100	0	0

10.3 Marginal Irregularities (Primary Outcome Measure 2)

With the USPHS criteria (Table 4), the margins of the restorations in both groups were scored as A, i, e., undetectable irregularities, at baseline, 6-months and 18-months follow-up.

With the FDI criteria (Table 5), the restoration margins of both groups were observed to be either excellent or good, i. e., either Score 1 or 2 (Table 6). No restorations were scored higher than 2 at all three time points. At Baseline, both groups have approximately similar percentages of restorations with Score 1 and 2. However, more restorations in Group 2 demonstrated longer lengths of Score 2 (10 - 20% of the perimeter length).

The Mann-Whitney U test was used to compare the prevalence of Score 1, Score 2a (<10% of the perimeter length) and Score 2b (10 – 20 % of the perimeter length) between the two groups. There were no statistically significant differences (P > 0.05) of the prevalence of the FDI Scores 1 and 2 between the two groups at baseline, 6-months and 18-months follow-up.

Score	Criteria
А	Undetectable.
В	Detectable. (V-shaped defect in enamel only or catches explorer going both ways).
С	Detectable. (V-shaped defect to DEJ).

Table 4 - USPHS Criteria for Marginal Adaptation / Irregularities

Table 5 - FDI Criteria fo	r Marginal	Irregularities
---------------------------	------------	----------------

Score	Category	Criteria
1	Clinically excellent	Harmonious outline, no gaps or white lines
2	Clinically good	Slight ditching, slight step, flashes or minor irregularities.
3	Clinically satisfactory	Multiple or major irregularities, ditching, flashes or steps.
4	Clinically unsatisfactory	Larger irregularities or steps. Repair necessary.
5	Clinically poor	Filling is complete- or partially loose but in situ.

Table 6 – Percentage of restoration in each group, with the respective FDI and USPHS scores for marginal irregularities, at baseline, 6- and 18-months follow-up.

		_	FDI Criteria (SQUACE)						USPHS criteria		
Time	Group	No of Particinant	1	2		3	4	5	А	В	С
point		1 articipant		а	b						
Deceline	1	18	38.9	44.4	16.7	0	0	0	100	0	0
Dasenne	2	18	44.4	33.3	22.2	0	0	0	100	0	0
6 months	1	16	75.0	25.0	0.0	0	0	0	100	0	0
0 monuis	2	17	70.6	23.5	5.9	0	0	0	100	0	0
18	1	14	57.1	42.9	0.0	0	0	0	100	0	0
months	2	13	53.8	30.8	15.4	0	0	0	100	0	0

a - <10 % of margin perimeter; b - 10 -20 % of margin perimeter

10.4 Patterns of OCT reflectance at the cavosurface angle and tooth-restoration interface. (Secondary Outcome Measure 1 - 3) at baseline.

Group	Elevated OCT reflectance at cavosurface angle	Elevated OCT reflectance at Tooth-Restoration Interface	Diminished OCT reflectance at the tooth- restoration interface
1	6.75 ± 6.36	16.20 ± 4.85	14.44 ± 4.36
2	1.56 ± 8.64	7.44 ± 5.29	18.75 ± 4.29

Table 7 – Percentage of the perimeter of the restorations at baseline, presenting with the following three patterns of OCT reflectance.

Mann-Whitney tests showed that there were significantly more (P < 0.05) elevated OCT reflectance at cavosurface angle and elevated OCT reflectance at tooth-testoration Interface debonding at the margins of the restorations in Group 1 compared to those in Group 2. There were no significant difference of the diminished OCT reflectance at the tooth-restoration interface of gaps between Group 1 and 2.

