2.0 Background

2.1 Research Question

A recent review of clinical studies published on the performance of posterior composite restorations that were recalled at least up to 24 months reported that the overall failure rate for studies conducted between 2006-2016 was 13.13% and the two main reasons for failure in these two decades remained the same, i.e. **secondary caries** (25.68% - 29.47%) and **composite fracture** (28.84% - 39.07%).¹ In *in vitro* studies, secondary caries has been attributed to interfacial gap or marginal defect both of which are consequences of polymerization contraction stresses. However, to date, **no clinical study** has been able to directly establish a link between these stresses (and its consequences) to secondary caries.²

World Dental Federation (FDI) and the United States Public Health Service (USPHS) clinical assessment criteria are the two main systems used to evaluate dental restorations in clinical trials. ^{3,4} Both systems are designed to evaluate different properties of a restoration and properties about marginal integrity have been reported to be the most frequent properties investigated of a resin composite restoration. The grading descriptions for these properties are subjective and the discrimination between grading and between properties (especially between marginal stains and secondary caries) is problematic. ⁵

Reasons for the lack of such a link are the discriminative deficiency of the clinical visual evaluation systems, the FDI and USPHS assessment criteria, and the ethical dilemma of restoration removal to assess for the presence or absence of secondary caries. It has been long acknowledged that an objective clinical measuring tool and new clinical study designs for secondary caries are needed to further the understanding of secondary caries initiation and progression and how these relate to the marginal integrity of dental restorations. This brings forth the need for a sensitive yet clinically applicable assessment method for interfacial debonding and demineralization.

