6.0 Study Flow

6.1 Study Design

This study is a randomized single-blind clinical trial and followed the Consolidated Standards of Reporting Trials (CONSORT) statement.

Each participant received only one composite restoration and the participants were blinded to the type of preparation technique used. The study dentist who completed the restoration was not blinded to the preparation technique because the form (shape) of the two types of preparations is distinctly different. However, the restoration evaluators will be blinded to the preparation design.

A HIPAA-compliant and browser-based electronic capture software, REDCap, was used for consent taking and research data recording and storage, including intraoral digital photographs. All data remained within REDCap and access was restricted to authorized personnel only. OCT scans were de-identified prior to uploading into BOX storage and linked to data in REDCap through study participant ID.

6.2 Screening Procedures

A UMN CTSI data pull, housed in a data shelter, was generated as a random query. A preliminary data screening was conducted by the PI using the random order provided and a preliminary list of patients that satisfy the Patient- and Tooth-level inclusion criteria was created. The patients were contacted via telephone to invite them to be a part of the study. If interested, a telemeeting was scheduled with a trained team member.

The telemeetings were conducted via Zoom and study information was shared with the potential participants using Microsoft PowerPoint slides and any arising questions arising were answered. For participants who did not have access to the internet or were able to devise access, they were called on a phone line. At the end of this telemeeting, an in-person screening appointment was scheduled for interested participants, and a packet containing the combined consent/HIPAA form, Guidelines and Consent for Unsecured Email Correspondence for Research Participants, and the study instruction sheet were mailed to them either physically or electronically.

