6.3 Dental Restoration Procedure

Participants were randomized into one of two groups using a randomization module incorporated in REDCap. Participants and evaluators were blinded to the assignment, but the study dentist was not.

Prior to scanning with OCT, the participants were instructed to brush their teeth. The fit of the OCT scan guide was then checked and adjusted if needed. Once the scan guide was properly positioned on the tooth that required restoration, excess saliva was removed using pressurized air. Next, the OCT intraoral probe was inserted into place, and pre-operative 3D OCT scans of the tooth were conducted. The scan rate was 20KHz and the scans took approximately 3-5 seconds depending on the size of the tooth. Laser safety glasses were worn by the participant and the operator.

The restorations for both groups were placed by one study dentist. Pre-operative occlusal contacts on intercuspal position and lateral excursions were marked with an articulating film and recorded. Local anaesthesia was then administered, and quadrant isolation was achieved with rubber dam. The Selective Caries Removal method was used in all cases except for cases where caries encroaches into the inner third of dentin, whereby the Partial Caries Removal method was performed. The Partial Caries Removal method was followed by lining of the pulpal floor with a thin layer of Dycal as an indirect pulp-cap material and light-cured glass ionomer (3M Vitrebond).

The cavity preparations were subsequently followed with either of the following techniques:

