Group 1 - Lesion-specific cavity design with 90° cavosurface angle throughout the cavity margins; Group 2 - Lesion-specific cavity design with wide bevel throughout the cavity margins was prepared. When cavity preparation is completed, the preparations in both groups were etched a 32% by weight phosphoric acid (3M ScotchbondTM Universal Etchant) on enamel and dentine for 15 seconds. After that, the etchant was rinsed away and an adhesive (3M ScotchbondTM Universal Adhesive) was applied on dentine and enamel with a microbrush for 20 seconds. The adhesive was light-cured for 10 sec with a curing light. Subsequently the preparation was restored in with a pre-warmed (using Bioclear Heatsync Kit) with a bulkfill resin composite (3M FiltekTM One Bulk Fill Restorative) and cured for 20 seconds according to the manufacturer's recommendation. The restorations were finished immediately with fine diamond burs and Sof-Lex XT coarse aluminum oxide disks (3M Oral Care). Polishing was carried out with the Sof-Lex Diamond Polishing System (3M Oral Care).

A post-operative 3D OCT scan of the restoration and the tooth was done using the same method as described above. Marginal integrity and staining of the restorations were evaluated using the FDI SQUACE criteria and the USPHS criteria. An intraoral digital photograph of the restoration was also taken.

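### Does the unexplained fall in FDI Score 2 by 6 months, with no evaluator agreement data, undermine the null result on marginal irregularity?

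*Combined protocol and SAP*

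**What the plan says.** Section 2.1 is open about the limits of the visual systems: "The grading descriptions for these properties are subjective and the discrimination between grading and between properties" is called problematic. The safeguard described is blinding. Section 6.1 says "However, the restoration evaluators will be blinded to the preparation design", and section 6.3 repeats it: "Participants and evaluators were blinded to the assignment, but the study dentist was not".

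Scoring is described in the same terms at each visit. After placement, "Marginal integrity and staining of the restorations were evaluated using the FDI SQUACE criteria and the USPHS criteria" (section 6.3); at 6 months, "Marginal integrity of the restorations and post-operative sensitivity were evaluated using the FDI SQUACE criteria and the USPHS criteria" (section 6.4), with the same procedure at 18 months (section 6.5). The documents do not state the number of evaluators, whether the same people scored each visit, or any calibration or agreement figure.

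Section 9.2 plans a Mann-Whitney comparison between groups at alpha 0.05. Section 10.3 gives the FDI irregularity scores in Table 6, comments on the baseline distribution, and reports "There were no statistically significant differences (P > 0.05) of the prevalence of the FDI Scores 1 and 2 between the two groups" at all three visits. In Table 5, Score 2 is defined as "Slight ditching, slight step, flashes or minor irregularities".

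**The concern.** Margins of composite restorations are usually expected to hold or deteriorate, yet the scores improved between baseline and 6 months. When a subjective grade improves without explanation, a reviewer asks whether the margins changed or the scoring did. The documents offer no agreement data to settle it, and section 10.3 passes over the fall.

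The stake is the reading of a null result. Staining on both systems and irregularity on USPHS were at the best grade for every tooth at every visit, so the primary comparison rests on FDI irregularity alone. Blinded scoring error that is equal in both groups tends to shrink a true difference. If the score were unreliable, a non-significant result could reflect the score and not the two preparation techniques.

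**Working it through.** **Inputs.** Table 6 percentages and denominators (section 10.3); one restoration per participant (section 6.1); three dropouts by 6 months (section 10.1), which the denominators split as two in Group 1 and one in Group 2.

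**Counts.** Each percentage times its denominator gives a whole number, and each row adds up.

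| Visit | Group 1: Score 1 / 2a / 2b | Group 2: Score 1 / 2a / 2b | Score 2, pooled |
|---|---|---|---|
| Baseline | 7 / 8 / 3 (n = 18) | 8 / 6 / 4 (n = 18) | 21/36 = 58.3% |
| 6 months | 12 / 4 / 0 (n = 16) | 12 / 4 / 1 (n = 17) | 9/33 = 27.3% |
| 18 months | 8 / 6 / 0 (n = 14) | 7 / 4 / 2 (n = 13) | 12/27 = 44.4% |

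**The reported tests.** Mann-Whitney on the ordered scores 1, 2a, 2b (normal approximation with tie and continuity corrections) gives P = 0.96 at baseline, 0.73 at 6 months and 0.64 at 18 months. All agree with the stated P > 0.05.

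**Forced improvement by 6 months.** The teeth at Score 1 at both visits cannot outnumber those at Score 1 at baseline. So the minimum number moving from 2 to 1 is the 6-month Score 1 count minus the baseline Score 1 count:

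- Group 1: 12 - 7 = 5 of 16
- Group 2: 12 - 8 = 4 of 17
- Total: at least 9 of 33 (27.3%), whatever the pattern of dropout. The largest number the table allows is 11 + 10 = 21.

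**Is the fall uneven between groups?** Score 2 goes from 11/18 to 4/16 in Group 1 (61.1% to 25.0%) and from 10/18 to 5/17 in Group 2 (55.6% to 29.4%). Both groups move the same way by a similar amount.

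**Forced improvement by 18 months.** The same bound gives 8 - 7 = 1 in Group 1 and none in Group 2 (7 is below 8). At the final visit the table forces almost no improvement from baseline.

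**How much could scoring error hide at 18 months?** Score 2 is 6/14 = 42.9% against 6/13 = 46.2%, a difference of 3.3 points (Newcombe 95% interval about -30 to +36). With equal error in both groups, the observed difference equals the true difference times (sensitivity + specificity - 1). The documents give no error rates. Assuming both at 0.9, then both at 0.8:

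- 3.3 / 0.8 = 4.1 points
- 3.3 / 0.6 = 5.5 points

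Both corrected point estimates are small beside the interval.

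**Power with 14 and 13 teeth** (exact enumeration of the same test, two-sided 0.05; all true rates are assumptions):

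| True Score 2 rates | Scoring error | Power |
|---|---|---|
| 20% v 70% | none | 79% |
| 20% v 70% | both 0.9 (26% v 66%) | 58% |
| 20% v 70% | both 0.8 (32% v 62%) | 36% |
| 30% v 60% | none | 37% |
| 20% v 50% | none | 38% |
| 30% v 50% | none | 19% |

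The loss from 79% to 36% looks severe only because it starts from a 50-point difference. For differences of 20 to 30 points, power is already 19% to 38% with perfect scoring.

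**The case for a change.** The strongest case for acting is that the documents themselves call the grading subjective, that blinding guards against bias but does not show reliability, and that the one informative primary score moved in an unexpected direction without comment. No refinishing after placement is described. Paired moves by group could be tabulated from existing data, and one sentence on the evaluators would cost nothing. A photograph was taken at each visit (for example "An intraoral digital photograph of the restoration was also taken" in section 6.4), so a masked re-scoring could be done.

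The facts in this stand: the fall is real and the evaluators are thinly described. The inference is weaker. Baseline was scored straight after finishing and polishing, and Score 2 includes flash and slight steps, which may be lost in function. Of the 21 baseline Score 2 teeth, 14 (8 + 6) were in the mildest band, under 10% of the perimeter, and all 36 were USPHS A. If the scoring threshold shifted instead, blinded evaluators would have applied the shift to both groups, so the comparison within that visit remains valid. Nor can visit-to-visit change measure agreement, because readings 6 months apart mix true change with error.

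Re-scoring photographs would not settle the matter: they miss tactile steps, may reveal a bevel, and would measure a different reliability from chairside scoring. The plan also adds OCT because visual grading is limited (section 2.1), although its results are reported only at baseline (section 10.4).

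**Conclusion.** No change to the plan follows. At least 9 of 33 teeth improved from Score 2 to Score 1 by 6 months, and the documents cannot say whether the margins or the scoring changed. Either way the shift is common to both groups under blinded scoring, and the reported P values reproduce. Evaluator detail, or a caveat beside the null, would make the report fuller but would leave every figure and test as it is. A reader can already see the fall in Table 6 and the acknowledged subjectivity in section 2.1.

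The main limit on the null is the sample: 27 teeth at 18 months and an interval of about -30 to +36 points. This conclusion assumes that blinding held and that any scoring error was similar in the two groups. Nothing in the documents contradicts either assumption, and neither can be verified from them.
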